7.2.3. Study Treatment Following the Primary PFS Analysis

Treatment assignments for all patients will be unblinded when the required number of PFS events for the primary PFS analysis at the end of Phase 3 have been obtained.

Patients who are on blinded study treatment at the time of the primary PFS analysis at the end of Phase 3 may proceed as follows:

- Patients in the placebo arm may cross over to open-label selinexor.
- Patients in the selinexor arm will continue selinexor but as open-label treatment.

All patients who have PD while receiving open-label selinexor will discontinue selinexor and be followed for survival, unless the Investigator, in consultation with the Sponsor, believes based on clinical judgement that the patient may derive benefit from continued treatment with selinexor (see Section 7.2.4).

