2.3. STUDY TREATMENT DOSING DATE

Study treatment dosing date is the date on which a patient actually received study treatment (selinexor or placebo, partial or complete).

For blinded treatment,

- Except for few patients who were randomized to selinexor in blinded treatment and entered open-label phase, the date of first study treatment is defined as the earliest date of non-zero dose of either selinexor or placebo. The date of last study treatment is defined as the latest date of non-zero dose of either selinexor or placebo before end of blinded treatment.
- For patients who were randomized to selinexor in blinded treatment and entered open-label phase, the date of first study treatment is defined as the earliest date of non-zero dose of selinexor, the date of last study treatment is defined as the latest date of non-zero dose of selinexor, regardless of blinded or open-label phase.

For open-label treatment, the date of first study treatment is defined as the earliest date of non-zero dose of open-label selinexor. The date of last study treatment is defined as the latest date of

non-zero dose of open-label selinexor. This definition only applies to patients who were randomized to placebo in blinded treatment and entered open-label phase.

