2.4. OBSERVATION PERIOD

For the patients who do not enter open-label selinexor, the observation period will be divided by the following:

- The pre-treatment period is defined as the time since the signed informed consent date up to the time before the date of first blinded study treatment.
- The blinded treatment period is defined as the time from the date of first blinded study treatment up to the date of last blinded study treatment + 30 days inclusive, or the day before initiation of a new anti-neoplastic treatment, whichever occurs first.
- The post-treatment period is defined as the time beyond the blinded treatment period.

For the patients who were randomized to placebo in blinded phase and entered open-label selinexor, the observation period will be divided by the following:

- The pre-treatment period is defined as the time since the signed informed consent date up to the time before the date of first blinded study treatment.
- The blinded treatment period is defined as the time from the date of first blinded study treatment up to the date of last blinded study treatment + 30 days inclusive, or the date of first open-label study treatment exclusive, whichever occurs first.
- The open-label treatment period is defined as the time since the date of first open-label study treatment to the date of last open-label study treatment + 30 days inclusive, (or the day before initiation of a new anti-neoplastic treatment, whichever occurs first).
- The post-treatment period is defined as the time beyond the open-label treatment period.

For the few patients who were randomized to selinexor in blinded phase and entered open-label selinexor, the observation period will be divided by the following:

- The pre-treatment period is defined as the time since the signed informed consent date up to the time before the date of first study treatment.
- The blinded treatment period is defined as the time from the date of first study treatment up to the date of last study treatment + 30 days inclusive, or the day before initiation of a new anti-neoplastic treatment, whichever occurs first. Please note that open-label selinexor is not considered a new anti-neoplastic treatment here.
- The post-treatment period is defined as the time beyond the blinded treatment period.

Please refer to Section 2.3 for the definitions of dates of first and last study treatment.

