5. SAFETY

Safety analyses will be reported by the actual treatment arm patients received and overall, among the Ph3-SAF and Ph2-SAF populations respectively. Unless otherwise specified, only data from the blinded treatment period will be presented. Please refer to Section 2.4 on definitions of observation periods.

For patients in the Ph3-OL and Ph2-OL populations respectively, selected safety data from the open-label period will be presented in separate summaries.

Safety analyses will be based on the reported AEs and other safety information, such as 12-lead electrocardiogram (ECG), vital signs, physical examination, ECOG performance status, clinical laboratory assessments including hematology and serum chemistry.

General rules

All safety analyses will be performed using the following common rules:

- Safety data in patients who do not belong to the safety population (e.g., enrolled but did not receive any dose of study treatment, partial or complete) will be listed separately.
- The baseline value is the last available value before first dose of study treatment. Please refer to Section 2.6 for details.
- The analyses of the safety variables will be essentially descriptive with no systematic testing planned.

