5.1.1.1. Treatment-Emergent Adverse Event (TEAE)

For AE summaries for blinded treatment period, treatment-emergent adverse events (TEAEs) are defined as any event that developed or worsened or became serious during the blinded treatment period, i.e., from the date of first blinded study treatment up to the date of last blinded study treatment + 30 days inclusive (or the day before initiation of a new anti-neoplastic treatment, whichever occurs first), or if applicable, the date of first open-label study treatment exclusive, whichever occurs first. Please refer to Section 2.4 on definitions on observation periods. Additionally, TEAEs also include any event that developed post the blinded treatment period but was assessed by the Investigator as related to study treatment. Please note for few patients who were randomized to selinexor in blinded phase and entered open-label selinexor, their blinded study treatment period ends on the date of last non-zero dose of open-label selinexor + 30 days inclusive. To these patients, open-label selinexor is not considered a new anti-neoplastic therapy.

For AE summaries for the open-label period, TEAEs are defined as any event that developed or worsened or became serious during the open-label treatment period, i.e., from the date of first open-label study treatment up to the date of last open-label study treatment + 30 days inclusive (or the day before initiation of a new anti-neoplastic treatment, whichever occurs first).

Additionally, TEAEs also include any event that developed post the open-label treatment period but was assessed by the Investigator as related to open-label selinexor. This definition applies to Ph3-OL and Ph2-OL populations only.

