5.1.2. Analysis Methods

The primary focus of AE reporting will be on TEAEs.

If an AE date/time of onset (occurrence or worsening) is incomplete, an imputation algorithm will be used to determine the AE as treatment-emergent. The algorithm for imputing date/time of onset will be conservative and will classify an AE as treatment-emergent unless there is definitive information to determine it is not treatment emergent. Details on classification of AEs with missing or partial onset dates are provided in Section 2.2.2.

AE summaries will include number (n) and percentage (%) of patients who have experienced an AE. The denominator for computation of percentages is the number of patients in the corresponding treatment arm. Multiple occurrences of the same event in the same patient will be counted only once in the tables.

Unless otherwise specified, sorting order will follow the alphabetic order in SOC, and further by decreasing frequency of PTs within each SOC. When more than one PT has same number of events, the order of presentation will be alphabetical in PTs.

Based on the entries on the eCRF AE page, an AE is considered related to study treatment if the entry for “Relationship to study treatment” is “Related” or “Possibly Related”.

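### The SAP's blinded treatment period for safety runs through open-label dosing on selinexor but stops at crossover on placebo, and adverse events are compared only as crude percentages

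*SAP*

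**What the plan says.** SAP 5 bases the safety tables on treatment received and states that, unless otherwise specified, "only data from the blinded treatment period will be presented". What counts as that period depends on the arm.

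- **Selinexor patients who enter open-label.** SAP 2.3: "the date of last study treatment is defined as the latest date of non-zero dose of selinexor, regardless of blinded or open-label phase". SAP 5.1.1.1: "their blinded study treatment period ends on the date of last non-zero dose of open-label selinexor + 30 days inclusive". Open-label selinexor does not end the window: "Please note that open-label selinexor is not considered a new anti-neoplastic treatment here" (SAP 2.4), repeated in SAP 5.1.1.1 as "To these patients, open-label selinexor is not considered a new anti-neoplastic therapy".
- **Placebo patients who cross over.** SAP 2.4 ends the window at the last blinded dose plus 30 days, "or the date of first open-label study treatment exclusive, whichever occurs first". Their later events go to separate open-label summaries. Those summaries are restricted to patients randomized to placebo (SAP 3.1.3), so selinexor-arm open-label events have no table of their own.
- **Patients who never enter open-label.** In either arm the window ends at the last blinded dose plus 30 days, or the day before a new anti-neoplastic treatment if that is earlier.

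On the measure, SAP 5.1.2 says "AE summaries will include number (n) and percentage (%) of patients who have experienced an AE", with the number of patients in the arm as denominator. Protocol 14.3.6.1 also uses patient incidence. Neither document plans a person-time, exposure-adjusted or time-to-event analysis of AEs. Duration of exposure is tabulated separately in SAP 3.4.1.

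**The concern.** A crude percentage is comparable between arms only if patients are watched for similar lengths of time. Here the rule lengthens the watch for some selinexor patients and shortens it for placebo patients who cross over. Both push the same way: selinexor looks worse relative to placebo, whatever the drug does. The label adds a second problem, because a table described as covering blinded treatment contains open-label treatment time, and only from the selinexor arm.

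These tables are the trial's main placebo-controlled safety comparison. The same period definition also feeds the summaries of deaths and, by the default in SAP 5, the worst-grade laboratory summaries.

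**Working it through.** **No plan figure to reproduce.** The documents give no AE rate, no exposure time and no count of selinexor patients who continue open-label. SAP 1.1 gives 285 patients randomized 2:1 in Phase 3, about 190 to 95.

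**Placebo tail, from the documents.** Protocol 9.2 requires the End of Blinded Treatment Visit within 14 days of the last blinded dose and the first open-label dose within 14 days of that visit. Crossover therefore starts at most 14 + 14 = 28 days after the last blinded dose, and a patient who crosses over on schedule always loses part of the 30-day tail.

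**Size, on assumed inputs.** Let λ be the same constant AE hazard in both arms, so there is no drug effect, with P(at least one event) = 1 − exp(−λT). Assumptions:
- blinded dosing of 3 months in both arms
- a 30-day tail of 0.986 month, so T = 3.986 for patients who never go open-label
- a share f of selinexor patients with X extra open-label months, so T = 3.986 + X
- a share c of placebo patients crossing over 14 days (0.460 month) after the last dose, so T = 3.460
- λ from 0.02 to 0.20 per month, f of 5–10%, X of 3–6 months, c of 50–80%

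*Selinexor extension alone* = f × [exp(−3.986λ) − exp(−(3.986 + X)λ)]:
- λ = 0.02, f = 5%, X = 3: 0.05 × (0.1304 − 0.0766) = 0.0027, or 0.3 points
- λ = 0.05, f = 10%, X = 6: 0.10 × (0.3930 − 0.1807) = 0.0212, or 2.1 points
- λ = 0.20, f = 10%, X = 6: 0.10 × (0.8643 − 0.5494) = 0.0315, or 3.1 points
- the maximum is near λ = 0.15: 0.10 × (0.5500 − 0.2236) = 0.0326, or 3.3 points

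*Shortened placebo tail alone* = c × [exp(−3.460λ) − exp(−3.986λ)]:
- λ = 0.02, c = 50%: 0.50 × (0.0766 − 0.0669) = 0.0049, or 0.5 points
- λ = 0.20, c = 80%: 0.80 × (0.5494 − 0.4994) = 0.0400, or 4.0 points

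*Both together*: mean time at risk is 4.1–4.6 months on selinexor and 3.6–3.7 on placebo (ratio 1.11–1.29), and the crude gap is 0.8 to 7.1 points.

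*If the affected group grows*, for example f = 30% and X = 6, the extension alone is three times the 10% result: 3.1 points at λ = 0.02 (3 × 1.04) and 9.8 points at λ = 0.15 (3 × 3.26).

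**What a common cut-off does.** Take λ = 0.05, f = 10%, X = 6, c = 80%. As planned, selinexor is 0.1807 + 0.0212 = 0.2019 and placebo 0.1632, a gap of 3.9 points. Now end both arms at the first open-label dose and treat selinexor continuers as having no tail, since their dosing is unbroken. Selinexor becomes 0.9 × 0.1807 + 0.1 × 0.1393 = 0.1766, and the gap falls to 1.3 points. It does not vanish, because more placebo than selinexor patients lose tail time. A rate per patient-year returns a ratio of 1 under the assumed equal hazard with either cut-off.

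**The case against.** The rule has a rationale. Protocol 12.1.3 says there is no break in dosing for selinexor patients who go open-label, and Protocol 14.3.6.1 counts treatment-emergent events to 30 days after the last dose of study treatment. Following continuous exposure is legitimate, and stopping placebo at crossover keeps selinexor events out of the placebo column. The safety analyses are descriptive, no decision rule depends on them, and the direction does not hide toxicity. All of this stands. It argues for keeping the continuous-exposure summary, but not for making it the only comparison or calling it blinded.

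Four stronger readings are tempting, and the documents do not support them.

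- **That the whole exposure difference between arms measures this defect.** With λ = 0.05, mean exposure of 5 versus 3 months and a one-month tail, 1 − exp(−0.05)/(1 + 0.05m) gives 23.9% versus 17.3%. That shows unequal exposure in general. It models neither the open-label extension nor the cut at crossover, and it should not be cited for this rule.
- **That post-unblinding reporting comes from one arm only.** Protocol 11.3.1 unblinds patients with progression in both arms, and a placebo patient who progresses without crossing over stays in the window for up to 30 days. What is one-sided is open-label treatment time. Placebo patients are also not wholly removed at crossover: SAP 5.1.1.1 still counts later events judged related to study treatment.
- **That every long-treated selinexor patient inflates the primary safety table.** Protocol 7.2.3 says "Patients in the selinexor arm will continue selinexor but as open-label treatment", but this follows the primary analysis, when SAP 1.6 already reports safety. At that cut the affected group is essentially those continued after progression under Protocol 7.2.4, whom the SAP calls few.
- **That the imbalance is invisible.** SAP 3.4.1 tabulates duration of exposure. It is simply not carried into any AE rate.

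**Conclusion.** The concern holds in limited form. The two windows are asymmetric on the face of SAP 2.3, 2.4 and 5.1.1.1, the label is wrong for part of the selinexor data, and nothing in the AE tables adjusts for time at risk.

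At the primary analysis the effect of the selinexor extension is probably small, roughly 0.3 to 3.3 points if 5–10% of the arm (about 10 to 19 of 190 patients) had 3–6 extra months. Those shares, durations and hazards are assumptions, and a constant hazard is itself a simplification. The actual number is not in the documents.

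The effect would be larger at the final analysis if the same definitions are applied there, because selinexor patients still on blinded treatment at the primary analysis then add open-label time. The SAP does not say how the by-arm AE tables will be handled at that point. This is an inexpensive improvement to the safety reporting; it touches neither efficacy nor type I error.

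**What to change.** 1. In SAP 5.1.2, add exposure-adjusted incidence rates per patient-year for the overview of treatment-emergent events, the serious events and the AEs of clinical interest.
2. In SAP 2.4 and 5.1.1.1, present the between-arm comparison with the period ending at the first open-label dose (exclusive) in both arms. Show selinexor-arm open-label events in their own table, as is already done for placebo crossovers.
3. Keep the continuous-exposure selinexor summary as a supplement, labelled as including open-label treatment.
4. State which version will be produced at the final analysis.

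Item 2 alone does not equalise time at risk, as the worked example shows, so item 1 is needed with it.

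The cost is SAP wording, programming on data already collected, and one or two extra tables, one of them for a small group at the primary analysis. Exposure-adjusted rates assume a roughly constant hazard, which is doubtful for events that cluster early in treatment, so they should accompany the crude percentages and not replace them.

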5.1.1.2. Serious Adverse Event (SAE)

An SAE is any untoward medical occurrence, at any dose, that:

- Results in death
- Is life-threatening (i.e., an event in which the patient was at risk of death at the time of the event; it does not refer to an event that hypothetically might have caused death if it were more severe)
- Requires inpatient hospitalization or prolongation of existing hospitalization
- Results in persistent or significant disability/incapacity
- Results in a congenital anomaly/birth defect

SAE needs to be clearly documented on the AE form. SAEs that occur at any time between the signing of the ICF up to the first dose of study treatment, must be reported (in addition to SAEs that occur after the first dose of study treatment).

5.1.1.3. Treatment-emergent Treatment-Related Adverse Events (TRAEs)

A TRAE is any TEAE that is assessed by the Investigator as related to study treatment.

For summaries on TRAEs for the open-label period, a TRAE is any TEAE that is assessed by the Investigator as related to open-label selinexor.

5.1.1.4. Adverse Event of Clinical Interest (AECI)

Any AE (serious or non-serious) that is of scientific and medical concern specific to the study treatment, for which ongoing monitoring and rapid communication by the Investigator to the Sponsor is appropriate.

5.1.2. Analysis Methods

The primary focus of AE reporting will be on TEAEs.

If an AE date/time of onset (occurrence or worsening) is incomplete, an imputation algorithm will be used to determine the AE as treatment-emergent. The algorithm for imputing date/time of onset will be conservative and will classify an AE as treatment-emergent unless there is definitive information to determine it is not treatment emergent. Details on classification of AEs with missing or partial onset dates are provided in Section 2.2.2.

AE summaries will include number (n) and percentage (%) of patients who have experienced an AE. The denominator for computation of percentages is the number of patients in the corresponding treatment arm. Multiple occurrences of the same event in the same patient will be counted only once in the tables.

Unless otherwise specified, sorting order will follow the alphabetic order in SOC, and further by decreasing frequency of PTs within each SOC. When more than one PT has same number of events, the order of presentation will be alphabetical in PTs.

Based on the entries on the eCRF AE page, an AE is considered related to study treatment if the entry for “Relationship to study treatment” is “Related” or “Possibly Related”.

5.1.3. Analysis of TEAE

An TEAE overview summary table will be provided, which will include the number of patients with at least one of the adverse events:

- TEAEs
- Grade 3/4 TEAEs
- Serious TEAEs
- TEAEs leading to dose modifications of study treatment
 - TEAEs leading to dose reduction of study treatment
 - TEAEs leading to dose interruption of study treatment
- TEAEs leading to study treatment discontinuation
- TEAEs leading to death
- TRAE
- Serious TRAEs
- TRAEs leading to dose modifications of study treatment

- TRAEs leading to dose reduction of study treatment
- TRAEs leading to dose interruption of study treatment
- TRAEs leading to study treatment discontinuation
- TRAEs leading to death

TEAEs will be summarized by primary SOC and PT and will include the following categories:

- All TEAEs
- All TEAEs, by maximum grade
- Grade 3 or higher TEAEs
- TEAEs leading to dose modifications of study treatment

The most commonly reported (at least 10% of all patients) TEAEs will be presented by PT only and will include the following categories:

- The most commonly reported TEAEs
- The most commonly reported TRAEs, a lower cut-off (e.g., 5% or 2% depending on TRAE frequency) will be used.

5.1.4. Analysis of SAE

Treatment-emergent SAEs will be summarized by primary SOC and PT and will include the following categories:

- All treatment-emergent SAEs
- All treatment-emergent treatment-related SAEs
- Treatment-emergent SAEs leading to dose modifications of study treatment
- Treatment-emergent SAEs leading to study treatment discontinuation
- All treatment-emergent SAEs leading to death

All SAE will be provided in a data listing.

5.1.5. Analysis of AECI

Standard MedDRA Query (SMQ), Customized MedDRA Query (CMQ), or specific Preferred Terms will be utilized for AECI analysis. Analyses of treatment-emergent AECI will be performed separately for each pre-specified AECI category. Overview summary of all AECI will be summarized similarly as in Section 5.1.3.

The following AECI will be summarized by PT:

- All TEAEs
- Serious TEAEs

The list of AECI categories are provided in Table 5-1. The search strategy of preferred terms for each category will be provided in a separate document.

Table 5-1 AECI Categories

Group Category	AECI Category
Hematologic events	Neutropenia
	Thrombocytopenia
Eye disorders events	Blurred Vision
	Cataract
Gastrointestinal events	Nausea
	Vomiting
	Decreased Appetite
	Weight Decreased
Infection	Pneumonia
	Sepsis
Metabolism and nutrition disorders	Hyponatremia
Nervous system disorders	Neurological Toxicity

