5. RATIONALE FOR THE STUDY

Nonclinical data indicate that selinexor shows cytotoxic effects at nanomolar concentrations on a variety of sarcoma cell lines, whereas non-cancer cells show cytotoxic effects at much higher concentrations of selinexor. In murine xenograft models, three times a week oral treatment with selinexor inhibits the tumor growth of a variety of sarcomas including liposarcoma.

Selinexor treatment resulted in SD in 30 of 52 (58%) evaluable patients with liposarcoma in the sarcoma Phase 1 study KCP-330-003 (Section 4.3.1). The most commonly reported TRAEs were nausea, fatigue, thrombocytopenia, anorexia, and hyponatremia, which were primarily Grade 1 or 2 (Section 4.3.4.1). Nausea and anorexia were well controlled with antinausea medications and appetite stimulants. These data further support the development of selinexor for the treatment of liposarcoma.

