- PD, as defined by RECIST v. 1.1 (see exception for patients who may derive benefit from continued treatment with selinexor in Section 7.2.4)
- Clinical progression, as determined by the Investigator in consultation with the Sponsor (must be documented by radiographic imaging and assessed by the central reader)
- Unacceptable AEs or toxicity that cannot be managed by supportive care
- Study treatment is discontinued at the discretion of the Investigator (see Section 11.2)
- Patient withdraws consent

Patients will be followed for survival (Section 9.1.8 and Section 9.2.6) until the end of the study, withdrawal criteria are met, or death.

Patients will also receive best supportive care to manage the main adverse drug reactions of selinexor, which are nausea, anorexia, and fatigue.

In order to minimize nausea, unless contraindicated, all patients must receive serotonin receptor subtype (5-HT3) antagonists (ie, ondansetron 8 mg or equivalent) starting on Day 1, before the first dose of blinded study treatment and continued, as needed, 2-3 times daily. In those patients in whom a 5-HT3 antagonist is contraindicated, olanzapine (5.0 mg at bedtime or 2.5 mg twice daily) is recommended based on Investigator experience during Phase 1 selinexor studies. Additional options can be found in the National Comprehensive Cancer Network (NCCN) Clinical Practice Guidelines in Oncology (CPGO) (NCCN CPGO) for antiemesis and anorexia/cachexia (palliative care).

Approximately 34 months will be required to complete the primary Phase 3 PFS analysis. The Phase 3 accrual period began immediately after enrollment of the Phase 2 portion was completed and will be approximately 30 months. The primary endpoint analysis will be performed approximately 4 months after enrollment of the last patient, once 209 PFS events have occurred, at which time all Phase 3 patients will be evaluable for assessment of the primary endpoint.

The Investigator may remove a patient from study treatment as described in Section 11. The Investigator must determine the primary reason for a patient's discontinuation of study treatment and record this information on the electronic case report form (eCRF). Patients who discontinue study treatment are not eligible to re-initiate treatment at a later date.

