12.2.5.2. Supportive Care

General Supportive Care Recommendations

Supportive measures for optimal medical care should be provided during participation in this clinical study. Based on clinical observations 1672 adult patients in Karyopharm-sponsored studies as of 31 March 2018, the main adverse drug reactions are primarily related to anorexia with poor caloric and fluid intake, fatigue, and nausea. Thrombocytopenia also occurs, although it is rarely associated with bleeding. Besides the required 5-HT3 prophylaxis (Section 12.2.5.1), supportive care including anti-nausea / anti-emetic therapy, acid suppression (proton pump inhibitors and/or H2-blockers) and other treatments may be administered as described below:

- a. Appetite stimulants: megestrol acetate at a dose of 80-400 mg daily.
- b. Centrally acting agents, such as olanzapine (5.0 mg at bedtime or 2.5 mg twice daily). Additional options, including D2 antagonists, can be found in the [NCCN CPGO](#) for antiemesis and anorexia/cachexia (palliative care).
- c. Neurokinin 1 receptor antagonist (NK1R antagonist): aprepitant or equivalent should be considered and will be covered for selected patients who have severe nausea and vomiting.

Supportive Care and Dose Adjustment Recommendations for Specific Selinexor-Related Adverse Events

Please see detailed recommendations in [Table 9: Supportive Care and Dose Adjustment Guidelines](#).

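### SAP 5.1.3 shows treatment-related events by term only above an open frequency cut-off, where the protocol plans a tabulation without one

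*SAP*

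**What the plan says.** **Protocol.** Section 14.3.6 names drug-related AE reports among the means of judging safety and has related AEs summarized per treatment group. Section 14.3.6.1 first says that AEs are displayed by SOC and PT. It then describes three summaries in sequence: TEAEs per group by SOC and PT, a tabulation of related TEAEs, and Grade 3 or higher TEAEs handled the same way as before. None has a frequency limit.

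**SAP 5.1.3.** The overview table counts patients with any TRAE. The four tables by SOC and PT are all of TEAEs: all, by maximum grade, Grade 3 or higher, and leading to dose modification. TRAEs by term come only in the common-event block, which opens with "The most commonly reported (at least 10% of all patients) TEAEs will be presented by PT only". For the TRAE table in that block, "a lower cut-off (e.g., 5% or 2% depending on TRAE frequency) will be used".

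**Elsewhere in the SAP.** Section 5.1.4 lists "All treatment-emergent treatment-related SAEs" by SOC and PT, and section 5.2 does the same for fatal TRAEs, both without a limit. The visible entries in SAP 1.7 cover endpoints that will not be analyzed and the per-protocol definition. None concerns AE tables.

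**Fatigue.** SAP 5.1.5 states "Analyses of treatment-emergent AECI will be performed separately for each pre-specified AECI category", and Table 5-1 lists 12 categories without fatigue. Protocol 7.1 refers to "the main adverse drug reactions of selinexor, which are nausea, anorexia, and fatigue", and protocol 12.2.5.2 says much the same. On the Phase 1 sarcoma study, protocol section 5 says: "The most commonly reported TRAEs were nausea, fatigue, thrombocytopenia, anorexia, and hyponatremia, which were primarily Grade 1 or 2".

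**The concern.** The protocol treats related events as a safety summary in their own right, beside all TEAEs and severe TEAEs. The SAP cuts their by-term display down to the frequent ones and leaves the meaning of frequent open until frequencies can be seen. Serious and fatal related events are protected by their own tables. Non-serious related terms below the limit have no TRAE row.

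If the limit is taken over both arms together, 2:1 allocation adds a second effect. A term seen only on selinexor is diluted by the placebo patients, so its rate on selinexor must be 1.5 times the nominal limit before it is shown. Drug-specific terms are the ones a TRAE table is meant to bring out.

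At stake is the completeness of one safety table. No hypothesis test or efficacy estimate depends on it.

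**Working it through.** The plan states no figure here to reproduce, so the check sizes what the cut-off can leave out.

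**Inputs**
- Phase 3: 285 randomized 2:1 (SAP 1.1). Arm counts and treated counts are not given. Assumed: all treated, split 190/95.
- Cut-offs of 5% and 2%, which are the SAP's own examples (5.1.3).
- Base of the cut-off: both arms pooled, if the opening words of the common-event block carry over to the TRAE table.

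**Pooled cut-off *c*, no placebo cases.** The selinexor rate needed is c × 285/190 = 1.5c, that is 7.5% at 5% and 3.0% at 2%. In whole patients, a term is shown from k = ceil(285c) cases, so up to k − 1 can be left out.

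- 5%: 285 × 0.05 = 14.25, k = 15; up to 14/190 = 7.4% left out.
- 2%: 285 × 0.02 = 5.7, k = 6; up to 5/190 = 2.6% left out.

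**Sensitivity to the assumptions**
- Two placebo cases: 12/190 = 6.3% at 5%; 3/190 = 1.6% at 2%.
- Planned 185/92, no placebo cases: 277 × 0.05 = 13.85, k = 14, 13/185 = 7.0%; 277 × 0.02 = 5.54, k = 6, 5/185 = 2.7%.

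**How much the open choice matters.** Take a term with a true selinexor rate of 5% and no placebo cases. With a binomial count on 190 patients, the chance of fewer than 15 cases is about 0.95, and the chance of fewer than 6 is about 0.08. The later choice between 5% and 2% largely decides whether such a term is shown.

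**If the limit applies in either arm instead**
- 5%: 190 × 0.05 = 9.5, so 10 selinexor cases are needed (or 5 of 95 on placebo); up to 9/190 = 4.7% left out.
- 2%: 190 × 0.02 = 3.8, so 4 selinexor cases are needed (or 2 of 95 on placebo); up to 3/190 = 1.6% left out.

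A 5% either-arm rule alone would therefore show fewer selinexor-only terms than the SAP's own 2% option (4.7% against 2.6% left out). That is why the fix below uses 2%. At the same percentage, over all count pairs for 190/95 and 185/92, no term shown by the pooled rule is hidden by the either-arm rule.

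**The 10% TEAE cut-off.** Pooled, it needs 29 cases (29/190 = 15.3%), but all TEAEs also have a full SOC/PT table, so nothing is lost there.

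**Fatigue.** Of the five most common Phase 1 TRAEs, four have a Table 5-1 category: nausea, thrombocytopenia, anorexia (as decreased appetite) and hyponatremia. Fatigue does not. Of the three main reactions in protocol 7.1, two are listed. Separate rows for fatigue and asthenia cannot be added to a patient-level rate, because one patient may have both. The documents give no rates from which to size this.

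**The case against.** The best defence is that the protocol's sentence on related TEAEs does not itself say by SOC and PT, so the single TRAE count in the SAP overview might satisfy it. That is a strained reading. The section opens by saying that AEs are displayed by SOC and PT, and the sentence stands between two by-term summaries. It does stand that the by-term requirement comes from context and is not explicit.

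It can also be said that display limits are ordinary SAP business and that nothing disappears. Every term is in the uncut TEAE table by arm, related SAEs and fatal TRAEs are shown in full, and the protocol plans by-patient listings of all AEs. All of this stands, and it keeps the point small. A full TEAE table still does not show which events the investigator judged related.

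Two further limits stand. The TRAE item does not restate its base, so pooling is inferred from the opening of the block. The 5% and 2% values are examples only.

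On fatigue, a reader might infer that the SAP wrongly omits a required category or leaves fatigue unreported. The documents support neither. An AECI is defined as "Any AE (serious or non-serious) that is of scientific and medical concern specific to the study treatment", which does not turn on frequency, and Table 5-1 also holds categories such as cataract and sepsis that the protocol does not call main reactions. Fatigue is shown by arm as a preferred term in the TEAE tables, enters the SAE tables if serious, and is measured by the QLQ-C30 fatigue scale.

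**Conclusion.** A cheap improvement. SAP 5.1.3 narrows the protocol's tabulation of related TEAEs to a table with an open cut-off, and no visible entry in SAP 1.7 records the change. The affected events are non-serious, non-fatal related terms below the limit.

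On a pooled base, with 190/95 treated and no placebo cases, the worst case is 14/190 (7.4%) at 5% and 5/190 (2.6%) at 2%. These are upper bounds, not expected losses, and they shrink with any placebo cases or with an either-arm base.

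A reader might infer that related events in general go unreported below the limit. That is too strong: the gap is confined to the by-term TRAE display of events that are neither serious nor fatal. The missing fatigue category is an optional refinement, supported by the listing of the other two main reactions.

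**What to change.** 1. Add to SAP 5.1.3 a table of all TRAEs by SOC, PT and treatment arm, with no cut-off.
2. If a common-TRAE table is kept, fix its limit in advance at 2% or more of patients in either treatment arm. Once the full table exists, this matters only for layout.
3. Optional: add a Fatigue category to Table 5-1, grouping fatigue and asthenia terms, so that the share of patients per arm with any such event can be read directly.

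The cost is SAP wording, one more table and a few rows, all from AE data already coded. No new data are needed. The downside is slightly longer tables.
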